9.2 Sample Processing, Storage, and Shipment

Refer to the lab manual for sample collection, processing, storage, and shipment information.

9.3 Assay Methodology

9.3.1 Biomarker Analysis (Tissue and Blood)

Formalin-fixed, paraffin-embedded tumor specimens will be stained with anti-PD-L1 monoclonal antibodies. PD-L1 will be scored as a percentage by two independent pathologists who are unaware of clinical data. PD-L1 staining as a predictive measure will be explored at various thresholds of positivity.

TILs (CD8+, CD4+, nuclear FOXP3+) will be quantified by immunohistochemistry and assessed on hematoxylin and eosin stained tumor sections. TIL subsets will be classified as intraepithelial (iTILs) or stromal (sTILs), where iTILs are defined as the percentage of lymphocytes in direct contact with tumor cells, and sTILs are defined as the percentage of lymphocytes relative to the tumor stroma. Scoring, as a continuous percentage, will be performed by two independent pathologists who are unaware of clinical data.

Population of CD4+, CD8+, and regulatory T cells (CD4+/CD25+) will be counted by cell sorting of PBMCs. Expression of CD4, CD8, and FOXP3 will be also examined in the tumor tissues to estimate relative ratio between T helper cells, killer T cells, and regulatory T cells.

Blood will be collected at C1D1, C3D1, and the End of Treatment visit for biomarker analysis.

9.3.3 Immune and Genomic Biomarkers

To assess the dynamic change in both immune and genomic biomarkers in blood that may correlate with response to veliparib. Blood will be collected prior to starting veliparib (Induction Day 1) and pre-dose on C1D1.

10.0 STATISTICAL CONSIDERATIONS

10.1 Study Design/Study Endpoints

This will be a phase I/IB study of nivolumab and veliparib in patients with advanced solid tumors and lymphoma harboring mutations in selected DNA repair genes.

The **primary endpoint** is to evaluate the toxicities and tolerability of nivolumab and veliparib and to identify the maximum tolerated dose for combination treatment.

Secondary endpoints include ORR according to irRECIST, PFS at 24 weeks, time until death or disease progression, and to identify additional predictive biomarkers and resistance mechanisms to treatment using additional genetic and immunology-based assessment platforms. For the preliminary efficacy analysis, ORR will be computed at the first imaging (8 weeks). Preliminary efficacy will be evaluated by RECISTv 1.1. As exploratory analysis, irRECIST will be used to obtain preliminary efficacy as well. All ORR will use the first imaging time point whether RECIST or irRECIST.

Exploratory endpoints include biomarkers predictive of response include assessment of tissue-based immunohistochemical expression of PD-L1; TILs; peripheral T cell subpopulations; changes in tissue and peripheral T cell receptor sequencing, HLA genotype, and immune-related candidate gene signatures at baseline.

Pharmacodynamic biomarker assessment will include changes in tissue based immunohistochemical expression of PD-L1; TILs; peripheral T cell subpopulations, and T cell receptor genotype at baseline and after two months of treatment with veliparib and nivolumab.

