4.0 TREATMENT PLAN

4.1 Overview

In Phase 1, patients will be treated with a dose escalation plan for veliparib based on a 3+3 study design. The initial patient cohort will be treated with veliparib 300 mg PO twice daily and nivolumab as follows (1 cycle = 28 days):

Cycle 1-4: 240 mg IV every 2 weeks and

Cycle 5+: 480mg IV every 4 weeks

See section 4.2 for treatment administration and dosing modifications based on the planned 3+3 study design. Total cycle length is 28 days (4 weeks). Combination treatment will continue until progression of disease or intolerability with scans occurring every 8 weeks (see section 4.7.1 for possible treatment beyond progression). Patients in the expansion cohort (Phase1B) will be treated with the MTD, that is now established. This same treatment plan will be used for patients in both the dose escalation and dose expansion cohorts.

Patients will undergo a fresh tissue biopsy prior to study enrollment, unless deemed to be clinically inappropriate per PI, to evaluate pharmacodynamic changes in immune-related biomarkers. Correlatives will be assessed as detailed in section 9.0.

[Please note: . According to the modified plan for the current trial, the study will be closed after the 6 additional patients in the expansion cohort will have been recruited.]

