- j. Imaging (either CT scan or MRI and PET if applicable) will be performed at screening, ≤ 28 days prior to registration. The same modality used at baseline should be used throughout for imaging. CT imaging will include chest, abdomen, and pelvis. Neck will be included only if measurable lesions are present. Scans will then take place every 2 cycles (8 weeks) starting with Cycle 3 Day 1 (- 7 days). Tumor measurements will be performed using RECIST 1.1 or Lugano classification. Progressive Disease (PD) must be confirmed by repeat scan within 8 weeks.
- k. Patients will undergo a fresh tissue biopsy prior to study enrollment, unless deemed to be clinically inappropriate per PI. If a fresh biopsy is not feasible, an archival tissue sample should be obtained (a cell block is preferred, however 15 unstained slides will suffice). Tissue should be obtained by any means possible, but patients will not be excluded from the study if tissue is not available. The samples will be obtained for correlative studies – see section 9.0 and separate lab manual for details.
- l. Study labs will be collected for tumor markers pre-dose on Induction Day 1, C1D1, C3D1, and at the End of Treatment visit. See section 9.0 and separate lab manual for more details.
- m. Nivolumab will be administered as follows:
 - Cycles 1-4: given at a fixed dose of 240mg IV over 30 minutes (-5 / +15 minutes) every 2 weeks
 - Starting with Cycle 5 Day 1: 480mg IV over 30 minutes (-10 / +15 minutes) every 4 weeks until disease progression, intolerability, or withdrawal of consent.
 - Vital signs will be monitored prior to, throughout, and after the nivolumab infusion according to Table 4.2.
- n. Veliparib will be taken orally at the assigned dose twice a day until disease progression, intolerability, or withdrawal of consent. It will be initiated as monotherapy during a 7-day induction period. Starting with Cycle 1 Day 1, veliparib will be given twice daily in combination with scheduled nivolumab infusions. Veliparib may be taken with or without food. Patients will be given a drug diary to maintain for compliance. Veliparib dosing may take place independently of nivolumab. On the day of a study visit, lab values should be checked against sections 4.4 and 4.5 for continued dosing.
- o. The end of treatment visit should occur 30 days after the last dose of study treatment (± 7 days) or before starting another line of treatment, whichever comes first.

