9.0 CORRELATIVES/SPECIAL STUDIES

9.1 Sample Collection Guidelines

Tissue: A fresh tissue biopsy of the primary tumor or a metastatic site at baseline will be collected if appropriate. If a fresh tissue biopsy is not feasible, archival tissue should be collected (if available, cell block preferred or 15 unstained slides) by any means possible. Unavailability of tissue will not exclude patients. Fresh tissue biopsies will be performed using an image-guided core needle at the aforementioned time points according to institutional practice. Tumor samples will be stored and may be used for additional correlative studies at a later date such as, but not limited to, immunohistochemistry, tumor mutation analysis, and proteomic analysis.

Blood: Blood samples will be drawn pre-dose on Induction Day 1, C1D1, C3D1, and at the End of Treatment visit. See lab manual for further details and tube types.

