10.3 Data Analyses Plans

The primary analysis will be on the intent-to-treat (ITT) population, including all evaluable patients. Clinical benefit rate will be defined as stable disease (for ≥ 12 weeks), complete or partial response by both the Response Evaluation Criteria in Solid Tumors (RECIST) and irRECIST or Lugano Criteria 2014. Maximum response prior to disease progression will be used. The overall response rate will be estimated by the proportion of overall response, and its 80% confidence..

Additionally, we will evaluate overall response rate, defined as complete or partial response using RECIST or Lugano Criteria 2014 guidelines in a similar manner. We will also perform similar analyses using Immune Related RECIST (irRECIST). Duration of response, defined as the duration from the first documentation of clinical benefit to the first documented progressive disease or death of any cause, whichever occurs first, will also be analyzed. For patients alive and progression-free at the time of data cut off, duration of response will be censored as of the last tumor assessment date. Duration of response will only be evaluated for the subgroup of patients with a clinical benefit using the Kaplan-Meier method.

PFS is defined as the time from treatment initiation to documented disease progression. OS is defined as the time from the start of treatment until death due to any cause. For patients alive at the time of data cut-off, PFS and OS will be censored as of the last tumor assessment date or known to be alive, respectively. The PFS and OS will be estimated using the Kaplan-Meier method. The number, frequency, and severity of adverse events (as defined by the NCI Common Terminology Criteria for Adverse Events or CTCAE version 4.03) will be recorded.

Baseline percent PDL1 expression, TILs (sTILs, iTILs, and their ratio), and changes in T

cell subpopulations will be used as a continuous variable to predict clinical benefit or overall response rates using appropriate statistical summaries. Cox proportional hazards regression will be used to compare how these biomarkers are associated with PFS and OS as well.

Changes in these biomarkers will also be analyzed to assess for pharmacodynamic effects of treatment. Continuous variables will be analyzed using either paired t-tests, signed rank tests or repeated measures analysis of variance.

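### Tissue change tests have no scheduled tissue pairs, and the T-cell change related to response, PFS and OS needs named draws and a C3D1 landmark

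*Combined protocol and SAP*

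**What the plan says.** **Planned change tests.** Section 10.1 lists "changes in tissue based immunohistochemical expression of PD-L1; TILs; peripheral T cell subpopulations, and T cell receptor genotype at baseline and after two months" of combined treatment. Sections 2.3.2 and 6.6.2 state the same pharmacodynamic aim, and 6.6.1 adds change in tissue T-cell receptor sequencing. For change in these biomarkers, 10.3 says: "Continuous variables will be analyzed using either paired t-tests, signed rank tests or repeated measures analysis of variance".

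**Tissue schedule.** Section 4.1 gives the purpose of the biopsy as "to evaluate pharmacodynamic changes in immune-related biomarkers". Table 5 marks the biopsy at Screening only, and its footnote k reads: "Patients will undergo a fresh tissue biopsy prior to study enrollment, unless deemed to be clinically inappropriate per PI". Section 9.1 says "A fresh tissue biopsy of the primary tumor or a metastatic site at baseline will be collected if appropriate", and later "Fresh tissue biopsies will be performed using an image-guided core needle at the aforementioned time points according to institutional practice".

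**Change as a predictor.** Section 10.3 has one sentence broken across a page: "Baseline percent PDL1 expression, TILs (sTILs, iTILs, and their ratio), and changes in T", continuing "cell subpopulations will be used as a continuous variable to predict clinical benefit or overall response rates using appropriate statistical summaries". The next sentence takes the same biomarkers into Cox models for PFS and OS, both timed from treatment start. No draws and no landmark are named.

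**Blood and scans.** Sections 9.3.1 and 9.3.2 list C1D1, C3D1 and end of treatment (EOT). Section 2.3, footnote l and 9.1 add Induction Day 1. Section 9.3.3 pairs Induction Day 1 with C1D1. Footnote j puts the first scan at C3D1 or up to 7 days earlier, and 10.1 fixes all ORR at that scan. Section 4.7.1 lets some patients continue treatment after progression that is not yet confirmed.

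**The concern.** A paired test needs two values per patient. PD-L1 and TILs are scored on tumor sections (9.3.1), so blood cannot stand in for the missing second sample. One stated analysis therefore has no planned data behind it.

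The T-cell change is a covariate that becomes known only after the clock for PFS and OS has started. If it is measured once the first scan is done, a patient's value may already reflect the outcome it is meant to explain. A consequence of progression could then be reported as a predictive marker. Four draws also allow 4 × 3 / 2 = 6 different changes, so leaving the choice open in a 15-patient study invites selection after the data are seen.

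**Working it through.** The plan gives no sample size, significance level or power for these analyses, so there is no figure of its own to reproduce.

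**Step 1: tissue.** Scheduled tissue time points: 1 (Table 5, footnote k, 9.1). The time points that 9.1 refers back to consist of baseline alone. A pair needs 2, so scheduled pairs are 0 of 9 enrolled + 6 planned = 15 patients. What tissue was actually collected from the first 9 is not reported.

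**Step 2: calendar.** Count Induction Day 1 as day 0.
- C1D1 = 7; C3D1 = 7 + 2 × 28 = 63.
- First scan = 63 − 7 to 63 = days 56 to 63.
- C3D1 sample minus scan = 0 to 7 days (nominal, before visit windows).
- Two months of combination treatment, C1D1 to C3D1, is 56 days. This matches the interval in 10.1.
- Stable disease for at least 12 weeks needs 84 days. C3D1 is 56 days after C1D1 and 63 after Induction Day 1, so this component is still open at C3D1.
- The Induction Day 1 to C1D1 change is known at day 7, before any on-study scan, and has no such problem.

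**Step 3: patients left at a C3D1 landmark.** With assumed exponential PFS of median m days, the progression-free share at day 63 is exp(−ln 2 × 63/m). For m = 60, 90, 120, 180 this is 0.483, 0.616, 0.695, 0.785. Times 15, that is 7.2, 9.2, 10.4 and 11.8 patients.

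**Step 4: size of the PFS bias, by simulation.** Assumptions: n = 15; no true effect of the marker on PFS; exponential PFS; up to 6 scans, one every 56 days; standard normal marker, shifted by d SD in first-scan progressors; a share s of those progressors has a value and the rest drop out; Cox score test with discrete-tie variance, two-sided 5%; 20,000 trials per cell. Rejection rates from treatment start, in %, for m = 60, 90, 120, 180:

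| s | d = 0.5 | d = 1.0 |
|---|---|---|
| 100% | 10.2, 9.5, 8.6, 7.8 | 26.9, 21.3, 17.9, 13.6 |
| 50% | 8.1, 7.4, 6.9, 6.5 | 16.9, 13.3, 11.7, 9.0 |
| 25% | 6.7, 6.3, 6.2, 6.1 | 11.3, 9.2, 8.4, 7.0 |
| 0% | 4.5, 5.4, 5.1, 5.6 | 4.5, 5.2, 5.7, 5.6 |

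With d = 0 the rate is 4.7% to 5.8% at every share. A C3D1 landmark uses the same patients as s = 0 and gives 4.5% to 5.7%. Restricting the patient set does the work: for a fixed set, moving the time origin left the Cox estimate unchanged.

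**Step 5: other tests, same shifts.**
- Efron ties, Wald (8,000 trials per cell): 7.2% to 22.6% (s = 100%), 5.7% to 12.6% (50%), 3.7% to 6.1% (25%), landmark 1.5% to 4.4%.
- Efron ties, score: 8.0% to 24.3%, 6.7% to 14.6%, 5.5% to 8.7%, landmark 3.2% to 5.8%.
- Breslow ties, score, s = 100%: 1.7% to 9.9%, against 0.7% to 3.3% with no shift.

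**Step 6: OS.** Add exponential post-progression survival (assumed median 120 or 240 days), with a value available for all patients. From treatment start: 6.4% to 10.2%. C3D1 landmark in all alive: 6.1% to 8.6%, or 5.6% to 6.3% when stratified by first-scan progression. With no shift, all versions give 5.8% to 6.4%. Between 13.6 and 14.7 of 15 patients are alive at the landmark.

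**The case against.** On tissue, the best defense is that sample collection is referred to a separate lab manual, which was not available for this review. That is a fair limit, but the protocol's own schedule contains no on-treatment biopsy. A reader might go further and infer that the pharmacodynamic objective as a whole is lost. It is not, because blood is drawn at C1D1 and C3D1 and can be tested.

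On the T-cell change, the defense is stronger, and most of it stands.
- The change is not wholly undefined. Section 10.1 gives two months for peripheral T cells, and 9.3.2 lists draws that make C1D1 to C3D1 the natural choice. What remains is that 10.3 does not say so.
- A reader might infer that EOT change will be used as a predictor, which could inflate false positives far more. No passage says this; EOT is only one of the listed draws.
- The Cox sentence speaks of association. The excess rejections are false only against a predictive reading. Sections 2.3 and 10.1 do, however, name predictive biomarkers as the goal.
- The shift, share, medians and significance level are all assumed. The 27% figure needs every first-scan progressor to have a C3D1 value. Section 4.7.1 makes that extreme, since decline in performance status or clinical signs of significant progression bar continuation.
- The documents name no tie method, and some methods give lower rates.

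The differing blood lists might be read as a contradiction. They mostly serve different objectives: the Induction Day 1 to C1D1 change belongs to 2.3.3 and 9.3.3.

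**Conclusion.** The tissue part is wrong as written: tests of tissue PD-L1 and TIL change are planned with no scheduled tissue pairs.

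The T-cell part is a cheap improvement rather than a demonstrated error. On the natural C1D1 to C3D1 definition, the value comes with or after the scan that fixes ORR, so it cannot predict that ORR. For PFS from treatment start the bias is conditional: about 6% to 27% false positives under the assumed 0.5 to 1.0 SD shifts when a quarter to all of first-scan progressors have a value. It is lower with some tie methods, and nominal with no shift or no such patients. For OS the effect is small.

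These analyses are mainly exploratory, although 10.1 also places predictive biomarkers among the secondary endpoints. A reader might infer that the main conclusions are at risk. The documents do not support that: the MTD, the ORR success rule, prediction from baseline PD-L1 and TILs, and the blood change tests are untouched.

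**What to change.** **Tissue.** In 2.3.2, 4.1, 6.6, 10.1 and 10.3, limit change analyses to blood and use tissue as a baseline predictor only. If the sponsor wants to keep tissue change, Table 5 and 9.1 must be made to agree with it.

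**T-cell change.** State in 10.3:
- T-cell change is C1D1 to C3D1 for all patients.
- PFS is analyzed from a C3D1 landmark in patients alive and progression-free at C3D1, with the first scan counted as before the landmark.
- OS is analyzed from C3D1 in patients alive with a C3D1 sample; stratifying by first-scan progression is optional.
- The link with first-imaging ORR is reported as an association, not a prediction.
- For clinical benefit, only the part decided after C3D1 (stable disease for at least 12 weeks) is treated as predicted.
- EOT change is not used as a predictor.

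**Minor.** Name the one baseline draw for T-cell change in 9.3 as well, and keep the Induction Day 1 to C1D1 change as a separate analysis.

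**Cost.** Wording only, with no new sampling. The price is precision for PFS: the landmark set falls to about 7 to 12 of 15 patients under the assumed medians. For OS about 14 of 15 remain, less any without a C3D1 sample.

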10.2 Sample Size and Accrual

The initial study has recruited 3 patients at the lower dose and 6 at the MTD. Of these 6 at the MTD, 4 have genetic mutation of interest, and 2 do not. The study will, due to lack of funding and other reasons recruit 6 more patients with genetic mutation of interest. The response rate will be computed separately for 4+6 = 10 patients with genetic mutation.

Dose Escalation Phase

The expected number of patients in the dose escalation phase will be in the range of 6 to

18 based on the 3+3 design.

Expansion Cohort

The initial study design was to accrue a total of up to 50 patients (for 48 evaluable) to the study in two phases: dose escalation and dose expansion. The original design anticipated a total of 6-18 patients with advanced solid tumors or lymphoma in the dose escalation phase; 9 patients were enrolled, including 6 that were treated at the MTD of 400 mg BID. Due to funding issues, the study will perform an early analysis of preliminary efficacy after the next 6 patients are enrolled in the expansion cohort.

As stated above, in **the modified plan for expansion cohort**, will accrue 6 new patients with genetic alteration for early preliminary efficacy assessment, which together with 4 previously treated patients with genetic mutation will provide total of 6+4=10 patients, with genetic mutation. ORR will be computed at the first imaging (8 weeks). Preliminary efficacy will be evaluated by RECISTv 1.1. As exploratory analysis, irRECIST will be used to obtain preliminary efficacy as well. All ORR will use the first imaging time point whether RECIST or irRECIST.

The study will be considered a success if the lower 90% exact confidence bound will be > 10% , i.e. if three or more successes out of n=10 are observed.

I According to the modified plan for the current trial, the study will be closed after the 6 additional patients will have been recruited.”

10.3 Data Analyses Plans

The primary analysis will be on the intent-to-treat (ITT) population, including all evaluable patients. Clinical benefit rate will be defined as stable disease (for ≥ 12 weeks), complete or partial response by both the Response Evaluation Criteria in Solid Tumors (RECIST) and irRECIST or Lugano Criteria 2014. Maximum response prior to disease progression will be used. The overall response rate will be estimated by the proportion of overall response, and its 80% confidence..

Additionally, we will evaluate overall response rate, defined as complete or partial response using RECIST or Lugano Criteria 2014 guidelines in a similar manner. We will also perform similar analyses using Immune Related RECIST (irRECIST). Duration of response, defined as the duration from the first documentation of clinical benefit to the first documented progressive disease or death of any cause, whichever occurs first, will also be analyzed. For patients alive and progression-free at the time of data cut off, duration of response will be censored as of the last tumor assessment date. Duration of response will only be evaluated for the subgroup of patients with a clinical benefit using the Kaplan-Meier method.

PFS is defined as the time from treatment initiation to documented disease progression. OS is defined as the time from the start of treatment until death due to any cause. For patients alive at the time of data cut-off, PFS and OS will be censored as of the last tumor assessment date or known to be alive, respectively. The PFS and OS will be estimated using the Kaplan-Meier method. The number, frequency, and severity of adverse events (as defined by the NCI Common Terminology Criteria for Adverse Events or CTCAE version 4.03) will be recorded.

Baseline percent PDL1 expression, TILs (sTILs, iTILs, and their ratio), and changes in T

cell subpopulations will be used as a continuous variable to predict clinical benefit or overall response rates using appropriate statistical summaries. Cox proportional hazards regression will be used to compare how these biomarkers are associated with PFS and OS as well.

Changes in these biomarkers will also be analyzed to assess for pharmacodynamic effects of treatment. Continuous variables will be analyzed using either paired t-tests, signed rank tests or repeated measures analysis of variance.

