
Treatment Plan
	
Patients will be treated using a dose escalation plan based on a 3+3 design. The starting dosing for veliparib will be 300 mg PO twice daily, and treatment will begin as monotherapy during a 7-day induction period. Patients in Phase Ib will be treated at the MTD.
 
Nivolumab combination therapy will begin Cycle 1 Day 1 as follows: Cycle 1-4: 240 mg IV every 14 days (Day 1 & 15) Cycle 5+: 480mg IV every 28 days (Day 1 of each cycle).
 
Combination treatment will continue until disease progression unacceptable toxicity, or withdrawal of consent.
 
This treatment plan is applicable for patients in both the dose escalation and dose expansion cohorts.

Statistical Methodology
	
The primary analysis will be based on toxicity and maximum tolerated dose. For all analyses, the intent-to-treat (ITT) population will be used to include all evaluable patients. Clinical benefit rate will be defined as stable disease (for ≥ 12 weeks) and complete or partial response by the Response Evaluation Criteria in Solid Tumors (RECIST). Lugano classification will be used for lymphomas. Maximum response prior to disease progression will be used. The overall response rate will be estimated by the proportion of overall response, and its 90% lower bound will be estimated using the exact binomial distribution. If this lower bound $> 10\%$ (ie. at least three responses are observed) the trial will be considered a success.
 
Additionally, we will evaluate overall response rate, separately for patients with and for those without genetic mutation entertained in this study, Early analysis of preliminary efficacy will be based on the patients with genetic mutation (n=10). Response is defined as complete or partial response using RECIST guidelines in a similar manner. We will also perform similar analyses using Immune Related RECIST (irRECIST). Duration of response, defined as the duration from the first documentation of clinical benefit to the first documented progressive disease or death of any cause, whichever occurs first, will also be analyzed. For patients alive and progression-free at the time of data cut off, duration of response will be censored as of the last tumor assessment date. Duration of response will only be evaluated for the subgroup of patients with a clinical benefit using the Kaplan-Meier method.

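### Duration of response is timed from first clinical benefit in every clinical-benefit patient, so patients with stable disease only, who are non-responders, enter the response-duration curve

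*Combined protocol and SAP*

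**What the plan says.** Section 10.3 uses two outcome categories:

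- Clinical benefit: "Clinical benefit rate will be defined as stable disease (for ≥ 12 weeks), complete or partial response".
- Overall response: "we will evaluate overall response rate, defined as complete or partial response using RECIST or Lugano Criteria 2014 guidelines".

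It then describes "Duration of response, defined as the duration from the first documentation of clinical benefit to the first documented progressive disease" or death, and sets the analysis population: "Duration of response will only be evaluated for the subgroup of patients with a clinical benefit using the Kaplan-Meier method".

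The Statistical Methodology row of the Study Summary has the same structure. There, "Clinical benefit rate will be defined as stable disease (for ≥ 12 weeks) and complete or partial response", "Response is defined as complete or partial response using RECIST guidelines in a similar manner", and duration of response again starts at first clinical benefit in the clinical-benefit subgroup. Sections 2.2.2 and 6.5.2 also define ORR as partial plus complete response. No section limits duration of response to responders or calls it duration of clinical benefit.

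**The concern.** A patient whose best result is stable disease for 12 weeks or more is a non-responder for ORR, yet contributes a time to the curve labelled duration of response. Three consequences follow:

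1. Patients with stable disease only enter the curve.
2. A patient who has stable disease first and responds later can have time before the response counted as response duration.
3. The start for a stable-disease patient is named (first documentation of clinical benefit) but cannot be applied without a further choice. The definitions in the Study Summary and Sections 2.2.2, 6.5.2 and 10.3 give 12 weeks without an origin, and the stable-disease criterion in Section 6.1.7 gives neither a duration nor an origin.

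What is at stake is the meaning of one reported summary. If nobody responds, the trial could still report a response duration. Durability is part of the protocol's rationale (Sections 1.1 and 1.8), and Section 1.7.2 quotes a median duration of response from an earlier nivolumab study. Readers are therefore likely to take the label at face value.

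**Working it through.** The documents give no median, precision or sample size for duration of response, so there is no figure to reproduce. The check compares the definitions and then bounds the effect.

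**Who enters the curve**

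| Best result | Response (ORR) | Clinical benefit | In the duration-of-response curve |
|---|---|---|---|
| CR or PR | yes | yes | yes |
| SD for at least 12 weeks | no | yes | yes |
| SD for less than 12 weeks, or PD | no | no | no |

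The second row is the contradiction.

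**Share with stable disease only**

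The Study Summary (Sample size) reports no response in the 6 patients already at the MTD, and 6 more are planned, giving 6 + 6 = 12. The success rule needs at least 3 responders among the 10 mutation-positive patients.

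- With 3 responders, the others at the MTD number 12 − 3 = 9: 7 mutation-positive patients and the 2 without the mutation. Between 0 and 9 of them could be stable disease only, so the share runs from 0% to at most 9/12 = 75%.
- In the 10 mutation-positive patients alone, the upper bound is (10 − 3)/10 = 70%.
- In all 15 patients (3 + 6 + 6), if those 3 are the only responders, it is (15 − 3)/15 = 80%. Responses in the 3 lower-dose patients are not stated.
- With no responder at the MTD, any MTD curve is 100% stable disease.

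**Start date for a stable-disease patient**

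Scans are every 8 weeks from Cycle 3 Day 1, with a −7-day window (Section 5.0, footnote j). Visits from Cycle 2 have ±3 days (Table 5). I assume that the −7 days apply to every scan and that visit shifts do not accumulate. Elapsed days from Cycle 1 Day 1:

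| Scan | Nominal | Range |
|---|---|---|
| Cycle 3 Day 1 (week 8) | 56 | 46–59 |
| Cycle 5 Day 1 (week 16) | 112 | 102–115 |
| Cycle 7 Day 1 (week 24) | 168 | 158–171 |

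Twelve weeks is 84 days.

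- Counted from Cycle 1 Day 1: 46–59 is below 84 and 102–115 is above it, so the week-16 scan is the first to document benefit.
- Counted from Induction Day 1 ("treatment will begin as monotherapy during a 7-day induction period", so add 7): 53–66 is below 84 and 109–122 is above it, so the same scan qualifies.
- Counted from the first stable-disease scan: the week-16 scan comes 102 − 59 = 43 to 115 − 46 = 69 days later, too early. The week-24 scan comes 158 − 59 = 99 to 171 − 46 = 125 days later, so week 24 qualifies.

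The week-16 and week-24 readings differ by 168 − 112 = 56 days, or 8 weeks. The range is 158 − 115 = 43 to 171 − 102 = 69 days, or 6.1 to 9.9 weeks. Back-dating to the week-8 scan, which the text does not state, also differs from the week-16 reading by a nominal 8 weeks. A 16-week gap (168 − 56 = 112 days) arises only between the two extremes.

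**Example.** A patient has stable disease at weeks 8 and 16 and a first partial response at week 24. Under the week-16 reading, 24 − 16 = 8 weeks before the response count as response duration. Under the week-24 reading, none do.

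**The case against.** The strongest reply is that the start point and the analysis population agree with each other. Both are written in terms of clinical benefit, so the plan describes a coherent duration of clinical benefit under the wrong name. The measure is missing from the objectives and endpoints in Sections 2 and 6, no decision depends on it, and at most 15 patients are involved. Renaming would remove the contradiction and keep something estimable, whereas a responders-only analysis may be empty.

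On the 12-week origin, Section 6.1 refers to RECIST v1.1, which may settle it. PFS and OS run from treatment start, which makes the week-16 reading the natural one. Nothing in the text points to week 24.

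Much of this stands. The point is limited in weight, renaming is a valid remedy, and the missing origin would be only a matter of detail on its own. The share of the curve due to stable disease is bounded, not known, and the bound depends on the population chosen. What does not stand is leaving the text alone: the label contradicts the definition of response in the same section, in both places. Favouring treatment start as the origin also does not write it into the plan.

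**Conclusion.** The concern holds. Following the plan as written puts patients with stable disease only into a duration-of-response estimate and can start a late responder's clock before the response. The share affected is unknown. At the MTD it is 0% to 75% with three responders and 100% of any curve with none. The start-date ambiguity is a nominal 8 weeks per stable-disease patient, resting on the scan-window assumptions above.

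This should be corrected, but it is a supportive descriptive summary. The MTD, ORR, PFS, OS and the three-of-ten rule do not change.

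**What to change.** Change the Study Summary and Section 10.3 together.

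- **Duration of response:** from first documented complete or partial response to progression or death, in those responders only. List individual durations if there are few, and give no estimate if there are none.
- **Which responders enter:** state whether response at the first scan only counts, as Section 10.1 has it for ORR, or response at any time before progression, as Section 10.3 implies with "Maximum response prior to disease progression will be used". Follow however that separate conflict is resolved.
- **If the present quantity is kept:** rename it duration of clinical benefit and report it separately. Start stable-disease patients at the first assessment that documents stable disease of at least 12 weeks. Count the 12 weeks from a named day, Induction Day 1 or Cycle 1 Day 1, the same day as time zero for PFS. On schedule both days select the week-16 scan.
- **Separate minor point:** Section 6.3.1 sets no minimum duration for immune-related stable disease, whereas Section 10.3 requires 12 weeks. Reconcile the two.

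No new data or visits are needed. The cost is a protocol amendment with regulatory review and approval by both companies (Section 11.2), which could be combined with other changes.

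The drawback is a tiny or empty responder set. If the 6 earlier MTD patients remain non-responders, the chances for the 6 new patients at assumed response rates p are:

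| p | No responder, (1 − p)^6 | At most 2 responders (binomial) |
|---|---|---|
| 10% | 0.9^6 = 53% | 98% |
| 20% | 0.8^6 = 26% | 90% |
| 30% | 0.7^6 = 12% | 74% |

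That is why individual listing is preferable to a curve.
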